11.4 STATISTICAL METHODS

11.4.1 PRIMARY ENPOINTS

11.4.1.1 SAFETY: The upper limit of a one-sided 95% confidence interval for the expected proportion of patients experiencing a Serious Adverse Event (SAE) is estimated by U, where

$$U = \frac{(2np + Z_{0.05}^2) + Z_{0.05}\sqrt{Z_{0.05}^2 + 4pn(1 \cdot p)}}{2(n + Z_{0.05}^2)}$$

Here "p" is the observed proportion of patients experiencing an SAE . The CyberKnife intervention will be considered to be safe if this study's result verifies that U is not above $20\%^{80}$.

11.4.1.2 EFFICACY: The lower limit of a one-sided 95% confidence interval for the expected proportion of patients experiencing biochemical disease-free survival (bDFS) is estimated by L, where

$$L = \frac{(2np + Z_{0.05}^2) \cdot Z_{0.05} \sqrt{Z_{0.05}^2 + 4pn(1 \cdot p)}}{2(n + Z_{0.05}^2)}$$

Here "p" is the observed proportion of patients experiencing bDFS in either

ACCP001.4

arm of the trial. The CyberKnife intervention will be considered to be effective if this study's result verifies that L is not below 93%.

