2.0 OBJECTIVES

PRIMARY OBJECTIVES: The primary safety goal of this study is to estimate, in both low-risk and intermediate-risk cohorts, the rates of acute and late grade 3-5 gastrointestinal and genitourinary toxicity observed during the five years following CyberKnife SRS for prostate cancer. The primary efficacy goal is to document the rate of biochemical Disease-Free Survival (bDFS), Phoenix and ASTRO definitions, at 5 years.

SECONDARY OBJECTIVES: to measure the following in the study population: Rates of local failure, distant failure, disease-free survival, disease-specific survival, and overall survival; quality of life (QOL) in generic and organ-specific domains; work effort required in treatment planning and delivery of CyberKnife SRS.

Patients will be followed annually to 10 years, to collect additional data for descriptive analysis.

3.0 **DEVICE**

Accuray, Inc. (Sunnyvale, CA), received FDA clearance in July 1999 to provide treatment planning and image guided stereotactic radiosurgery and precision radiotherapy for lesions, tumors and conditions of the brain, base of skull and cervico-thoracic spine, head and neck using the CyberKnife. On August 10, 2001, Accuray, Inc. received 510(k) FDA clearance (510(k) number K011024) to provide treatment planning and image-guided stereotactic radiosurgery and precision radiotherapy for lesions, tumors, and conditions anywhere in the body when radiation treatment is indicated.

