11.0 STATISTICAL CONSIDERATIONS

11.1 OVERVIEW: This study's primary goal is to determine the rate of acute and late grade 3-5 gastrointestinal and genitourinary toxicity following CyberKnife treatment, and to estimate efficacy, measured as 5-year bDFS. Per RTOG/ECOG, acute toxicity will be defined as occurring within 90 days of completing treatment. Late toxicity will be defined as toxicity occurring more than 90 days after treatment. It is graded based on Common Terminology Criteria for Adverse Events (CTCAE) v3.0.(see appendix V).

11.2 SAMPLE SIZE:

11.2.1 PRIMARY SAFETY OBJECTIVE: The study is designed to test the null hypothesis that the acute and late GI/GU toxicity rate 5 years following treatment is greater than 10% versus the alternative hypothesis that the toxicity rate is less than or equal to 10%. The sample size is determined such that there is 90% probability, or power, of identifying excessive toxicity if the true toxicity rate is 20% at the one-sided 5% significance level. 101 patients must then be accrued and followed for 5 years, assuming no patients excluded or lost to follow-up. Since the treatment volume for intermediate risk patients is larger than for low-risk patients, the study will be powered to assess toxicity for both subgroups. Additional enrollment for ineligible patients, or lost to follow-up: Since performing central review of pathology prior to enrollment is impractical, some patients will be upgraded, and thus made ineligible. In RTOG 77-06, central review upgraded about 8% of Gleason 2-6 patients to Gleason 7-10⁷⁵. If we assume a similar rate of upgrading, and anticipate 8% additional ineligible/lack-of-data cases, sample size must be

- increased by 1/(0.92*0.92) = 119.33. Thus 120 patients are required to establish acceptable toxicity for each risk cohort.

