11.4.2 SECONDARY ENDPOINTS

- 11.4.2.1 QUALITY OF LIFE ASSESSMENTS: The SF-12 scores. AUA score, EPIC-26 scores are used to quantify quality of life (QoL) at baseline and repeatedly during the post treatment period (see Section 9.0). We will use the generalized estimating equation (GEE) method to provide valid inferences. This method was originated to make inference about average behaviour, where the dependent variable depends not only on the "explanatory" variable (time measured in months) but also on the correlation of a patient's repeated measurements. The GEE approach fits the model to the observed data as closely as possible, weighting each patients' "cluster" of measurements over time inversely to its variance – covariance matrix. With this method, no imputations are required and all data recorded is use in the analysis. Other important features of GEE are that no distributional assumptions for the dependent variable are required to use the method and in most cases valid inferences are provided even when the correlation structure is miss-specified. For each score, we will use GEE to fit a model to patients' longitudinal course of repeated values. We hypothesize that immediately following treatment, the GU & GI subsections of the EPIC-26 and the AUA will demonstrate a worsening of GU and GI function, but this will return to normal with time. We further hypothesize that the sexual function subset of the EPIC-26 will show gradual worsening function relative to baseline over the five-year follow-up period. These QOL outcomes will be compared to those reported in other prospective studies using the same instruments, including RTOG 0232 and 0415
- 11.4.2.2 ADVERSE EVENTS: All adverse events will be recorded on the case report forms. For both acute (<=90 days of treatment start) and late (>90 days of treatment start), the frequency and proportion of each type of adverse event will be presented in tabular form, on both a per-patient and a per-event basis.

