- Adverse Events: An unanticipated adverse effect is defined by the FDA as any serious adverse effect on health or safety or any life-threatening problem or death caused by, or associated with, a device, if that effect, problem, or death was not previously identified in nature, severity, or degree of incidence in the protocol (including a supplementary plan), or any other unanticipated serious problem with a device that relates to the rights, safety, or welfare of subjects. Should any unanticipated adverse device effects occur during the course of the study, the clinical monitor will ensure that they are documented by the investigator and reported to the sponsor and the reviewing Institutional Review Board (IRB) as soon as possible, but no later than ten working days after the investigator first learns of the effect(s). The report regarding any unanticipated adverse device effect also will be provided to all other IRBs for the sites at which this clinical evaluation is being conducted. The clinical monitor, on behalf of the sponsor, will work with one of the lead site's investigators and Accuray's medical monitor to conduct an evaluation of such effects. Following this evaluation, if the determination is made that an unanticipated adverse effect presents an unreasonable risk to subjects, the clinical evaluation will be paused, if deemed appropriate

(to enable further investigation) or terminated as soon as possible. Termination shall occur no later than five working days after the sponsor makes the determination and no later than 15 working days after the sponsor receives notice of the unanticipated adverse device effect. In the event of termination, IRB approval will be obtained prior to resuming the clinical evaluation.

12.5 Below are criteria for early termination of either arm of the trial should an excessive number of patients experience a Serious Adverse Event (SAE). This depends upon the number so far enrolled and a criterion that identifies too high a rate. The stopping criteria differ after 48, 96 and 120 patients have been enrolled in both groups with additional applications when up to 144 and 178 have been enrolled in the low-risk group. Consistent with Section 11.2.1, we define an observed SAE rate of 20% as too high The statistical requirement is that for up to "m" patients enrolled, the number of observed SAEs must be few enough so that there is a 95% chance that the "true" rate does not exceed 20%.

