	Serious Adverse Event (SAE) Stopping Criteria					
Participants to	Independently for both low- and interm-risk arms, stop an arm if					
be enrolled: 298	the number of grade 3-5 effects for that arm equals or exceeds:					
(178 low-risk,	Enrollment 1-48: 6 SAEs					
120 interm-risk)	Enrollment 1-96: 14 SAEs					
	Enrollment 1-120: 18 SAEs					
	Enrollment 1-144: 22 SAEs					
	Enrollment 1-178: 28 SAEs					

12.6 Regulatory Reporting: Any reports regarding safety issues and potential safety issues will also be provided to Accuray's Regulatory Affairs Department. Such reports will be evaluated and reported to the FDA and all applicable regulatory agencies, as deemed required.

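### The primary safety rule counts patients with an undefined SAE instead of patients with grade 3-5 GI/GU toxicity, the stated endpoint

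*Combined protocol and SAP*

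**What the plan says.** - **Endpoint.** Section 2.0 sets the primary safety goal, in both risk cohorts, as estimating "the rates of acute and late grade 3-5 gastrointestinal and genitourinary toxicity observed during the five years following CyberKnife SRS". Section 11.1 repeats it: "to determine the rate of acute and late grade 3-5 gastrointestinal and genitourinary toxicity following CyberKnife treatment", graded by CTCAE v3.0.
- **Hypothesis and sample size.** In Section 11.2.1 the null is that "the acute and late GI/GU toxicity rate 5 years following treatment is greater than 10" per cent. The alternative for power is 20%, with 90% power and a one-sided 5% level. This gives 101 evaluable patients, raised to 120 per cohort. The grade is not repeated there, but the GI/GU limit is.
- **Decision rule.** Section 11.4.1.1 takes the upper limit U of a one-sided 95% interval for the "expected proportion of patients experiencing a Serious Adverse Event (SAE) is estimated by U" and declares the treatment safe if U is not above 20%. It names no organ system, grade, toxicity scale or time window.
- **Nearest thing to a definition.** Section 12.5 says "Consistent with Section 11.2.1, we define an observed SAE rate of 20% as too high", and its stopping table applies when "the number of grade 3-5 effects for that arm equals or exceeds" a listed count. Neither has a GI/GU limit. Section 12.4 defines unanticipated device effects only.
- **Reporting.** Section 11.4.2.2 states that "All adverse events will be recorded on the case report forms", with tabulation by type and per patient.

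**The concern.** The objective and the hypothesis concern one event, and the rule that settles them counts another. The result depends on how an analyst reads SAE:

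- **Any grade 3-5 event**, as the table in 12.5 suggests. Grade 3-5 events outside the GI and GU systems, accumulated over five years, count against the treatment. An acceptable treatment becomes harder to declare safe.
- **Regulatory seriousness**, the usual meaning of the term. Grade 3 GI/GU toxicity that does not meet seriousness criteria may drop out, so an excessively toxic treatment could pass.

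The two readings push the verdict in opposite directions, so neither is a safe default. With no definition fixed in advance, the choice could be made after the data are seen. What is exposed is the formal verdict on a primary objective; the underlying data are still collected.

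**Working it through.** **Inputs.** Reference rates 10% and 20%, and n = 101 and 120 (Section 11.2.1); n = 150 evaluable low-risk patients (11.2.2); enrolment of 129 intermediate-risk and 190 low-risk patients (11.2.5); the formula for U and its 20% limit (11.4.1.1). The documents give neither a rate of grade 3-5 events outside GI/GU nor the share of GI/GU toxicities that are serious, so both are assumed over a range.

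**1. The plan's sample size.** n = [(1.645·√(0.10·0.90) + 1.282·√(0.20·0.80)) / 0.10]² = [(0.4935 + 0.5126)/0.10]² ≈ 101.2, against 101 stated. Then 101/(0.92·0.92) = 119.33, rounded up to 120. Both reproduce, and both are for GI/GU toxicity.

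**2. The pass limit.** U = [2np + z² + z·√(z² + 4np(1−p))] / [2(n + z²)], with z = 1.645 and z² = 2.706.
- 13/101: [26 + 2.706 + 1.645·√(2.706 + 45.307)] / 207.41 = 40.10/207.41 = 19.3%, pass.
- 14/101: 42.45/207.41 = 20.5%, fail.
- Likewise 21/150 gives 19.3% and 22/150 gives 20.04%, so the limit is 21.

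P(safe) below is the exact binomial P(X ≤ 13 | 101) or P(X ≤ 21 | 150).

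**3. Other events also counted, true GI/GU rate 10%.** Combined risk = 1 − 0.90·(1 − u), where u is the assumed proportion of patients with other counted events, taken as independent.

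| u | Combined risk | P(safe), n = 101 | P(safe), n = 150 |
|---|---|---|---|
| 0 | 10.0% | 87% | 96% |
| 1% | 10.9% | 79% | 91% |
| 3% | 12.7% | 59% | 73% |
| 5% | 14.5% | 38% | 49% |
| 10% | 19.0% | 7% | 7% |

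At the planned and enrolled sizes, with u = 5%, P(safe) falls from 91% to 42% (n = 120), from 94% to 49% (n = 129) and from 99% to 59% (n = 190).

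**4. The same with a low GI/GU rate (3%, assumed), n = 101.** Combined risk = 1 − 0.97·(1 − u). P(safe) is at least 99.7% for u = 1-3%, then 97%, 59%, 13% and 1% for u = 5%, 10%, 15% and 20%.

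**5. Regulatory reading only, true GI/GU rate 20%, no other events.** Counted risk = 0.20·s, where s is the assumed share of affected patients who meet seriousness criteria.

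| s | Counted risk | P(safe), n = 101 | P(safe), n = 150 |
|---|---|---|---|
| 1 | 20% | 4% | 4% |
| 0.75 | 15% | 33% | 42% |
| 0.5 | 10% | 87% | 96% |

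**The case against.** The strongest reply is that SAE is loose shorthand for the declared endpoint. Section 11.2.1 states the hypothesis as well as the size, 11.4.1.1 sits under the primary endpoints, and 12.5 ties its 20% limit back to 11.2.1. On that view this is a drafting slip. The intent is probably as described, but the text does not carry it through. The table in 12.5 supplies the grade and not the GI/GU limit, and the reference to 11.2.1 attaches to the 20% rate, not to a definition of the event.

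Second, on the grade 3-5 reading the error is only conservative. Every patient with a grade 3-5 GI/GU event also has a grade 3-5 event, so passing on the wider count implies passing on GI/GU. This is correct: on that reading the chance of a false safe verdict is not raised, and the cost is lost power. The false-safe figures in step 5 apply only to the regulatory reading, which the table in 12.5 argues against.

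Third, the large losses need a GI/GU rate near 10% or frequent other events. This also stands. At 3% GI/GU toxicity with few other events the harm is negligible, and the one graded CyberKnife series cited in Section 1.11 had no grade 3 or 4 toxicity in 26 patients.

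Fourth, a definition might sit in the case report forms, which Appendix IV only links and which could not be checked. The decision rule should not depend on that.

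Finally, the GI/GU proportion can be calculated from recorded data. That limits the damage, but a table does not settle which event decides the verdict.

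**Conclusion.** The concern holds and should be corrected before the primary safety analysis. As written, 11.4.1.1 does not test the endpoint in 2.0 and 11.1 or the hypothesis in 11.2.1. This is a defect of definition: the plan's arithmetic reproduces.

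The mismatch itself needs no assumption. Its size does. On the better-supported reading (any grade 3-5 event) the consequence is a lower chance of declaring an acceptable treatment safe: 87% down to between 79% and 7% at n = 101 and 10% GI/GU toxicity, for assumed independent other-event rates of 1% to 10%. On the regulatory reading the chance of passing a treatment at 20% rises from 4% to 33% or 87% at n = 101, for assumed seriousness shares of 75% or 50%. The rule's 20% bound is taken as written throughout; how it relates to the 10% null in 11.2.1 is a separate matter.

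**What to change.** In Section 11.4.1.1, define p, separately for each risk cohort, as the proportion of patients with at least one acute or late CTCAE v3.0 grade 3-5 GI or GU toxicity within five years of treatment. Every element of that definition is already in Sections 2.0, 11.1 and 11.2.1. Define SAE separately and report all SAEs with the other adverse events under 11.4.2.2.

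Section 12.5 uses SAE in its text and grade 3-5 effects in its table. The sponsor must reconcile the event counted there with 11.2.1 and 11.4.1.1; no particular stopping rule is proposed here.

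The cost is an edit to the wording. Toxicity is already evaluated at every scheduled follow-up (Section 9.0) and all adverse events are already recorded. The sample size stays at 101 evaluable patients per cohort, raised to 120. With the corrected event and 101 evaluable patients, the rule passes a treatment at 20% with probability 4.3% and one at 10% with probability 86.9%.

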- 9.3.2 EXPANDED PROSTATE CANCER INDEX COMPOSITE (EPIC)-26: is a validated comprehensive instrument developed to assess patient function and bother after prostate cancer treatment. It was developed by an expert panel of urological oncologists, radiation oncologists (including those with brachytherapy expertise), survey researchers, and prostate cancer nurses, to address symptoms related to radical prostatectomy, external beam radiotherapy, prostate brachytherapy, and hormonal symptoms. See appendix VI.
- 9.3.3 AMERICAN UROLOGICAL ASSOCIATION (AUA) SYMPTOM INDEX: Also known as the International Prostate Symptom Score (IPSS), this widely used index assesses urinary symptom bother. See appendix VI.
- 9.3.4 SEXUAL HEALTH INVENTORY FOR MEN (SHIM): is a widely used, internationally validated and sensitive instrument for assessing erectile dysfunction⁷⁰.
- 9.3.5 UTILIZATION OF SEXUAL MEDICATIONS/DEVISES: provides context for interpreting the sexual domain score of the EPIC questionnaire.
- 9.4 CRITERIA FOR DISEASE CONTROL: intervals will be measured from enrollment date.
 - 9.4.1 BIOCHEMICIAL DISEASE-FREE SURVIVAL (bDFS): is measured as time to PSA failure. While earlier reports of prostate cancer patients treated with radiotherapy have used the ASTRO consensus definition (ACD) of PSA failure, recent studies^{71,72,73} have suggested the "nadir+2" definition is a more sensitive and specific definition of biochemical failure. Indeed, a recent expert panel met in Phoenix⁷⁴ and developed a consensus recommendation using the later definition. So that comparisons can be made with earlier literature, both definitions shall be used:
 - 9.4.1.1 Phoenix definition: failure occurs when the PSA is ≥ 2 ng/ml more than the lowest PSA measurement before the current one, with no backdating. Administration of salvage therapy (hormones, surgery, etc...) will be considered failure.
 - 9.4.1.2 Strict ASTRO Consensus Definition (ACD): failure is defined as three consecutive rises in post-treatment PSA, measured at the specified follow-up intervals. If three consecutive PSA rises occur during the first 2 years after treatment, followed by a non-hormonal induced PSA decline, this will not be considered a failure. Administration of salvage therapy (hormones, surgery, etc...) will be considered failure. Failure date is the midpoint between the dates of the last non-rising PSA and the first PSA rise.

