- 11.2.2 PRIMARY EFFICACY OBJECTIVE: For the low-risk cohort, the study is powered to compare 5-year bDFS rates observed with CyberKnife to 5-year bDFS rates reported with dose-escalated external beam RT. In Beaumont's monotherapy HDR series treating LR patients, 5-yr ASTRO bDFS was 98%; in Demanes' series of 75% LR and 25% IR, this was 96%. We would expect Phoenix outcomes to be slightly higher than ASTRO outcomes at 5 years. Since CK delivers doses similar to HDR monotherapy, a conservative estimate of the success rate for CK is 97.5% for LR patients. In LR patients, prospective studies from Memorial Sloan Kettering⁷⁶ (203 patients, 81Gy) and MD Anderson⁷⁷ (32 patients, 78Gy) demonstrated 5-vr bDFS (Phoenix definition) of 92% and 93%, respectively. Thames' 9-institution review of 231 dose-escalated (70-76Gy) LR patients reported 94% 5-yr Phoenix bDFS. Thus, an objective performance criteria (OPC) for lowrisk patients treated with dose-escalated external beam RT is 93% 5-yr bDFS. Assuming the CK success rate is 97.5%, to test superiority of CK against this OPC with 80% power at the 1-sided 5% significance level will require 150 patients. Increasing the sample size by 1/(0.92*0.92) for ineligible/lack-of-data cases yields 177.22; the required sample size for low-risk patients is 178 patients.
- 11.2.3 TOTAL AND RELATIVE ENROLLMENT OF RISK GROUPS: Per sections 11.2.1 11.2.2, enrollment of 178 low-risk patients are required to compare the 5-year bDFS rate observed with CyberKnife to the 5-year OPC rate, and 120 intermediate risk patients are required to establish acceptable toxicity for each risk cohort. CaPSURE data showed a ratio of low to intermediate risk patients, using D'Amico's definition⁷⁸, of 46.8%:37.2%. This CK protocol excludes intermediate risk patients with both PSA 10-20ng/ml and Gleason 7 histology. Based on proportions of patients in these subgroups reported in Partin's⁷⁹ study, this would exclude 12% of intermediate risk patients. Combining these proportions, we would expect a ratio of low to intermediate risk patients of 1.43: 1. Thus we would expect 172 low-risk patients enrolled by the time 120 intermediate risk patients have been enrolled. Each cohort will be closed to accrual once requisite enrollment is achieved: 178 low-risk patients, and 120 intermediate risk (298 total patients)

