11.3 INTERIM ANALYIS FOR FUTILITY

When at least 50% of the Low Risk subjects have reached the 3 year time point, an interim analysis will be performed for the primary efficacy hypothesis to determine if it is futile to continue with study follow-up through 5 years. The primary efficacy study objective is to establish with 95% confidence that the 5 year bDFS rate is >93% (the OPC). For the interim analysis the 3 year bDFS rate will be used along with the same OPC of 93%.

11.3 1. Methodology:

The determination of 3 year bDFS will be made for all subjects with sufficient data through 3 years. Next, the probability of meeting the efficacy object at 3 years will be determined using simulation. Results for the subjects w/o sufficient data through 3 years will be simulated using a binomial distribution. The assumed probability of success (i.e. bDFS) will be set at the rate that was observed for the subjects w/ 3 year data. The simulation will be run 1,000 times resulting in 1,000 complete datasets. The lower confidence interval limit for 3 year bDFS rate will be calculated, using the Wilson method, for each dataset, and probability of success will be the proportion of datasets where the lower confidence limit is below 93%.

11.3.2.Rule:

If the probability of having a successful study is less than found to be less than 20% then it will be considered futile to continue with follow-up through 5 years.

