- 11.4.2.3 SURVIVAL OUTCOMES: "Survival" analyses will be performed for the outcomes defined in Section 9.4. These include Local and Distant tumor Control, Disease-free survival for measures listed in Section 9.4.3.2, Disease-specific survival for measures including those listed in Section 9.4.3.3, and Over-all survival for death from any cause. Periodically over the extended follow-up period, Kaplan-Meier "survival" curves will be calculated (examples: at 6 months, yearly, 5 years, at end of patient follow-up). From the Kaplan-Meier curve, descriptive statistics will be calculated including estimates of survival rates and mean and quartile survival times.
- 11.4.2.4 WORK EFFORT: At each site and for each patient, time spent actively involved with planning and treatment shall be recorded for all member of the treatment team (therapist, physicist, radiation oncologist, and urologist). The required on-site supervisory time will also be recorded. Average times will be recorded. Time spent by team members will be compared and correlated with other outcomes (e.g. experience level of team member, patient enrollment, treatment planning/delivery QA outcomes,

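### Both 5-year primary tests use a crude proportion with an undefined n and no rule for men lost or dead before 5 years, although bDFS is defined as a time to event

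*Combined protocol and SAP*

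**What the plan says.** Section 9.4.1 says that bDFS "is measured as time to PSA failure". The listed failures are a PSA rise and salvage treatment: "Administration of salvage therapy (hormones, surgery, etc...) will be considered failure". Death is not listed.

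Section 11.4.1.2 then decides efficacy from a single proportion. The one-sided 95% lower limit for the "expected proportion of patients experiencing biochemical disease-free survival (bDFS) is estimated by L", and the treatment counts as effective if L is at least 93%. Section 11.4.1.1 uses the mirror-image upper limit U for toxicity, with success if U is at most 20%. Both define p as an observed proportion. Neither defines n or mentions men whose 5-year status is unknown.

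Three other places bear on this:

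- Sections 11.2.1 and 11.2.2 size the trial on 101 and 150 men and then inflate. They "anticipate 8% additional ineligible/lack-of-data cases", on top of 8% for pathology upgrading. For efficacy, "Increasing the sample size by 1/(0.92*0.92) for ineligible/lack-of-data cases yields 177.22".
- Section 11.3.1 has a rule for the interim: "Results for the subjects w/o sufficient data through 3 years will be simulated using a binomial distribution". The final analysis has no counterpart.
- Section 11.4.2.3, under secondary endpoints, says that survival "analyses will be performed for the outcomes defined in Section 9.4". It adds: "From the Kaplan-Meier curve, descriptive statistics will be calculated including estimates of survival rates". It does not link these curves to the 93% or 20% criteria.

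**The concern.** Over 5 years some men will withdraw, be lost or die without the event. A crude proportion needs a rule for each of them, and the possible rules do not agree in direction or in error rate. Because the efficacy margin is a matter of one or two failures, the choice can decide the trial, and at present it could be made after the data are seen. The endpoint is defined as a time to event and dated PSA and toxicity assessments are collected, so an estimator that uses partial follow-up is already within reach.

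**Working it through.** **1. The plan's own figures.** With n = [(z_α√(p0(1−p0)) + z_β√(p1(1−p1)))/(p1−p0)]²:

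- Efficacy (93% v 97.5%, one-sided 5%, 80% power): [(1.6449×0.25515 + 0.8416×0.15612)/0.045]² = 149.97, so 150.
- Safety (10% v 20%, one-sided 5%, 90% power): [(1.6449×0.3 + 1.2816×0.4)/0.1]² = 101.2, against the stated 101.
- Inflation: 150/0.92² = 177.22 (178) and 101/0.92² = 119.33 (120).

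All reproduce. After the upgrading allowance alone, 178×0.92 ≈ 164 low-risk men remain, and 120×0.92 ≈ 110 per cohort for safety. The extra men in Section 11.2.5 (to 190 and 129) cover 5-alpha reductase users and hormone-exposed men, so 164 and 110 stay as working numbers.

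**2. What the Wilson rule allows (exact binomial).**

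| n | Most failures that pass | Type I error at 93% | Power at 97.5% |
|---|---|---|---|
| 140 | 4 | 2.9% | 72.7% |
| 150 | 5 | 4.5% | 82.5% |
| 164 | 6 | 5.5% | 88.1% |
| 178 | 6 | 3.1% | 84.0% |

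For safety, at most 13 events pass at n = 101 (86.9% chance of success at a true 10%) and 15 at n = 110 (91.9%).

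**3. The verdict can flip.** Take 164 men, 6 failures and 13 lost (8%).

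- Lost men kept in n: L = [2×158 + 2.7055 − 1.6449√(2.7055 + 4×158×6/164)]/[2×166.7055] = 310.35/333.41 = 0.9308. Passes.
- Lost men dropped, n = 151: L = [2×145 + 2.7055 − 1.6449√(2.7055 + 4×145×6/151)]/[2×153.7055] = 284.36/307.41 = 0.9250. Fails.

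**4. Direction of bias under each rule.** Assume constant hazards and independent loss of 8% by 5 years. At a true 97.5%, known event-free men are 0.975×0.92 = 0.8970. Failures seen before loss are [0.02532/(0.02532+0.08338)]×(1−0.8970) = 0.0240.

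- *Drop lost men, keep earlier failures:* 0.8970/(0.8970+0.0240) = 97.4%. The same sum turns a true 93% into 92.7% and a true 10% toxicity into 10.4%. Conservative.
- *Drop every man not followed to 5 years, earlier failures included:* unbiased under independent loss, but follow-up is discarded.
- *Count lost men as event-free:* a true 93% reads 93.3%. Anti-conservative.

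**5. Size.** Simulation with exponential event and loss times. Kaplan-Meier uses the Wilson formula with an effective n. Results are averaged over N = 154–174 (efficacy) and N = 101–119 (safety) to smooth discreteness. The 15% and 20% columns are assumed; the documents give only the combined 8%.

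| | 8% loss | 15% | 20% |
|---|---|---|---|
| Efficacy power: drop lost, keep earlier failures | 78.2 | 71.8 | 67.4 |
| Efficacy power: drop all not followed | 80.5 | 77.0 | 74.8 |
| Efficacy power: Kaplan-Meier | 82.7 | 80.9 | 79.3 |
| Efficacy type I error: Kaplan-Meier | 4.1 | 4.1 | 4.1 |
| Efficacy type I error: lost counted event-free | 5.2 | 6.6 | 7.9 |
| P(safe) at true 10%: drop lost, keep earlier events | 84.3 | 78.1 | 72.7 |
| P(safe) at true 10%: drop all not followed | 87.2 | 84.5 | 82.4 |
| P(safe) at true 10%: Kaplan-Meier | 88.5 | 87.3 | 86.3 |

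At single values of N, power when lost men are dropped and earlier failures kept, against Kaplan-Meier:

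- N = 164: 79.6/70.4/68.5% against 80.0/81.5/80.4%.
- N = 178: 82.4/76.4/71.0% against 86.0/84.9/82.7%.
- Safety at 110 men: 84.2/77.9/73.4% against 88.5/87.2/86.7%.

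If lost men count as event-free at 8% loss, efficacy type I error is about 7% at N = 164 (5.5% with no loss) and between 4 and 4.5% at N = 178 (3.1% with no loss). The false-safe rate at 110 men is about 8%.

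**6. Deaths and the choice of limit (N = 164).** With 4% deaths (assumed), power is 81/73/71% if the dead stay in n as non-failures, 76/69/66% if they are dropped as well, and 81/80/78% for Kaplan-Meier. The limit also matters: the untransformed Greenwood interval has type I error of 7.6/9.0/9.4%, and the complementary log-log limit 3.1/3.9/3.8%.

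**The case against.** A reader might infer that the plan biases bDFS downward and toxicity upward, because the sizing inflates for men without data and so seems to remove them. The documents do not support that. The inflation concerns head count. No section says that lost men leave n while their counterparts with earlier failures stay, and that asymmetry is what creates the bias. Removing everyone without 5-year follow-up is equally open, is unbiased under independent loss, and at N = 164 with 8% loss has about 82% power, slightly above Kaplan-Meier there. Nor does any section count lost men as event-free, so a claim that the plan inflates type I error would also overreach.

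The size is modest too. The inflation already pays for the expected missing men, so dropping them leaves power near the planned 80%, and the second 8% includes ineligible men, so pure loss may be lower. At 15% loss and N = 164 much of the gap is discarded men and discreteness: 140 complete men would have only 72.7% power. Part of the safety shortfall is present with no loss at all (86.9% at 101 men). Kaplan-Meier is not always ahead: with 8% deaths kept in n and 8% loss, the crude test has 82.5% against 81.6%. Section 14.7 lets withdrawn men be asked to continue PSA tests, and Section 11.2.5 allows enrolment to be adjusted.

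All of this stands as a limit on size and direction. It does not supply the missing n. Section 14.7 may reduce loss but defines no analysis, and accrual is planned to finish in 14 months (Section 11.2.4), before 5-year loss can be seen.

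**Conclusion.** The concern holds as a gap with a cheap improvement. Both primary decisions rest on a proportion whose denominator is not defined, for an efficacy endpoint that the protocol itself defines as a time to event. The effect may be conservative, neutral or anti-conservative depending on a rule that is not written, and one plausible data set passes under one rule and fails under another.

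At the planned 8%, dropping lost men while keeping earlier events costs about 0 to 5 points of efficacy power, depending on N, and about 4 to 5 points for safety, relative to Kaplan-Meier. Costs of about 8 to 14 points belong to a sensitivity range of 15 to 20% loss that is assumed. All sizes rest on constant hazards and independent loss. The change should be made before the 5-year analysis; the planned sample size does not need to be reopened for it.

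**What to change.** *Section 11.4.1.2.* Base the test against 93% on the Kaplan-Meier 5-year bDFS, S, in the low-risk cohort for which Section 11.2.2 powers it, censoring at the last PSA. Report it for both definitions in the primary objective (Section 2.0), noting that the 93% criterion was derived from Phoenix results. Prespecify the one-sided 95% lower limit as the existing Wilson formula with p = S and n = S(1−S)/Var(S), Var(S) from Greenwood (if there are no failures, n = number followed to 5 years), or a complementary log-log limit. Do not use the untransformed Greenwood interval. State how death without PSA failure is handled; censoring is consistent with Section 9.4.1.

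*Section 11.4.1.1.* Use the 5-year cumulative incidence F of the primary toxicity event, with death as a competing event, and the matching Wilson-type upper limit with n = F(1−F)/Var(F) against 20%. Sections 2.0 and 11.1 describe that event as grade 3-5 GI/GU toxicity while Section 11.4.1.1 speaks of SAEs; reconcile the two.

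*Cost.* SAP wording and some programming; no new patients, visits or data. The price is an assumption of non-informative censoring, which should be stated and tested in a sensitivity analysis, and the acceptance that the method is not more powerful in every scenario.
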